10.3 Secondary Analysis

For COPD:

Intraclass correlation coefficient (ICC) and Bland Altman plots will be used to assess the validity of the free-living data based TUG time estimator and the Virtual TUG time estimator. ICC will be used to evaluate the agreement in free-living metrics between study watch and reference device (Step Watch). 41

The test-retest reliability of below algorithms will be assessed by looking at repeated estimates from the algorithm (e.g., week-over-week) and compared with the test-retest reliability of the in-clinic clinician measured 6MWT distance.

The algorithms are mainly developed using data collected from other sources, however, a small set of pre-selected data will be used to refine these algorithms.

For PD:

ICC will be used to evaluate the agreement in free-living metrics between study watch and reference device (Step Watch).

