2.2 Secondary objectives

For COPD:

- 1) To analytically validate algorithms that utilize free living data to estimate the outcome of in-clinic Timed-up-and-go test (TUG) and obtain analytical validation of the algorithms;
- 2) To analytically validate algorithms that utilize virtual TUG to estimate the outcome of in-clinic TUG and obtain analytical validation of the algorithms;
- 3) To evaluate analytical validity of algorithms capturing various aspects of walking that utilize passively recorded sensor data; and
- 4) To obtain test-retest reliability of the following algorithms based on weekly Virtual 6MWT between first and second visits:
 - Free-living data based 6MWT distance estimator
 - Virtual 6MWT distance estimator
 - Free-living data based TUG time estimator
 - Virtual TUG time estimator.
 - Free-living walking measurements

A small set of pre-selected data will be used to refine the algorithms that are mainly developed using data from other sources.

For PD:

- 1) To obtain the dataset to develop algorithms that utilize free living data to estimate the outcome of in-clinic Timed-up-and-go test (TUG); and

- 2) To obtain the dataset to develop algorithms that utilize virtual 6MWT context-known data to estimate the outcome of in-clinic Timed-Up-and-Go test (TUG).
- 3) To obtain the dataset to evaluate analytical validity of free-living walking measurements utilize passively recorded sensor data.

COPD and PD participants will wear StepWatch and Study Watch at home over two weeks. This will provide a dataset to compare free-living data based walking measurements by the two devices. StepWatch will be used as a reference device to evaluate the performance of Study Watch walking measurements to quantify waking activity and walking capacity in at home settings.

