At the first, and subsequent visits to the clinic, required assessments and measurements are performed as described in Table 2. In-clinic assessments are repeated every 5 weeks. After each visit, participants are asked to fill out the following questionnaires: FACIT-Fatigue, EQ-5D-5L, Epworth Sleepiness Scale, HADS, LAPAQ outdoor, MDS-UPDRS part I (PD-only), MDS-UPDRS part II (PD-only), PDQ-39 (PD-only), CCQ (COPD-only). All questionnaires will be completed once within 14 days after each visit (either digitally in the Baseline platform or on paper) except for the FACIT-Fatigue and System Usability Survey, which will be completed weekly and only once after Visit 3, respectively. Unless specified as PD-only or COPD-only, questionnaires are for both PD and COPD cohorts. Participants will perform the virtual 6MWT and TUG at home using the Study Watch one time per week. The day and time of the week on which the tests are performed are standardized (i.e. same day + time of the week) while they are wearing the watch for up to 23 hours a day. For StepWatch device at home, the device will be provided, and participants will be asked to wear it simultaneously with the Study Watch for two weeks, between Visits 2 and 4. For those who are willing and consented to wearing a Fitbit device, the device will be provided, and participants will be asked to wear it simultaneously with the Study Watch on the opposite wrist for the first five weeks between the first and second visits.

Table 2. Overview of study consents, assessments for COPD and PD cohorts

Exams, Tests and Data Collection	Pre Visit	Visit 1 (Baseline)	Visit 2 (5th wk)	Visit 3 (10th wk)	Visit 4 (15th wk)	After each visit	Weekly at home
Visit Window		Day 0	In the 5th week	In the 10th week	In the 15th week	Within 7 days after each visit	
Screening consent	X						
Demographic information	X	X					
Pre-visit platform survey	X						
Inclusion/Exclusion criteria		X					
Study consent		X					
Medical history*		X	x				
Change in health status between visits			X	X	X		
User experience survey						X (at home, post visit 3 only)	
Post-visit platform survey					X		

User feedback on Study Watch					X		
Skin tone (Fitzpatrick Scale)		X					
Arm Hair Index		X					
Concomitant Medications		X	X	X	X		
Physiotherapy			X	X	X		X (self-training at home)
Adverse Events			X	X	X		
Exams, Tests and Data Collection	Pre Visit	Visit 1 (Baseline)	Visit 2 (5th wk)	Visit 3 (10th wk)	Visit 4 (15th wk)	After each visit	Weekly at home

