In Clinic Assessments & Surveys							
6MWT with pre & post Borg Scale (two times per clinic visit)		X	X	X	X		
TUG		X	X	X	X		
10MWT with single context (three times per clinic visit)		X	X	X	X		
10MWT with dual context (three times per clinic visit)		X	X	X	X		

Montreal Cognitive Assessment (MoCA)		X			X		
MDS-UPDRS Part I Rater Questionnaire (PD only)		X	X	X	X		
MDS-UPDRS Part III (PD only)		X	X	X	X		
MDS-UPDRS Part IV (PD only)		X	X	X	X		
Hoehn and Yahr Scale (PD only)		X	X	X	X		
COPD ABCD categorization (mMRC, COPD only)		X	X	X	X		
In Clinic Vitals & Measurements							
Pre-6MWT (#1&2) Resting blood pressure, SpO ₂ , heart rate		X	X	X	X		
Post 0 minute -6MWT (#1&2) SpO ₂ , heart rate		X	X	X	X		
Post 1 minute -6MWT (#1&2) SpO ₂ , heart rate		X	X	X	X		
Post 2 minute -6MWT (#1&2) SpO ₂ , heart rate		X	X	X	X		
Height, weight, leg length		X					

Exams, Tests and Data Collection	Pre Visit	Visit 1 (Baseline)	Visit 2 (5th wk)	Visit 3 (10th wk)	Visit 4 (15th wk)	After each visit	Weekly at home
At-home Clinical Assessments & Surveys**							
Virtual Walk Tests on the Study Watch (virtual 6MWT & TUG)							X
FACIT-Fatigue (13-item)							X
EQ-5D-5L						X	
Epworth Sleepiness Scale (ESS)						X	
Hospital Anxiety and Depression Scale (HADS)						X	
LASA Physical Activity Questionnaire (LAPAQ)						X	
MDS-UPDRS Part I & Part II Patient Questionnaires (PD only)						X	
Parkinson's Disease Quality of Life Questionnaire (PDQ-39, PD only)						X	
Clinical COPD Questionnaire (CCQ, COPD only)						X	

Optional Fitbit at home use		X (first 5 weeks, at home, 23 hours per day between visit 1 and visit 2)					
StepWatch at home use		X (for two weeks, at home; within the two weeks wearing the device at least 10 days, which can fall on any random day with a minimum of two weekend days. Wear time of four to six hours on these days).					

**Medical history will be collected during both visit 1 and visit 2*

*** These can be done in-clinic or at-home based on participant's preference.*

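### Section 10.3 benchmarks the reliability of every COPD algorithm on in-clinic 6MWT distance: the wrong test for the TUG estimators, and with no clinic repeat at the one-week interval it names

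*Combined protocol and SAP*

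**What the plan says.** In the COPD part of section 10.3 the relevant sentence begins "The test-retest reliability of below algorithms will be assessed", but no list follows. The list is in section 2.2, under the objective "To obtain test-retest reliability of the following algorithms based on weekly Virtual 6MWT between first and second visits". It names the free-living and virtual 6MWT distance estimators, the "Free-living data based TUG time estimator", the virtual TUG time estimator, and the free-living walking measurements.

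Section 10.3 bases the assessment on "repeated estimates from the algorithm (e.g., week-over-week") and says that the result is to be "compared with the test-retest reliability of the in-clinic clinician measured 6MWT distance". It names no TUG comparator for reliability. It does not say which clinic repeats form the benchmark, and it gives no reliability statistic or success criterion. Section 8.1.2 lists test-retest agreement as the third COPD secondary endpoint.

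On the clinic schedule, section 8.3 states "In-clinic assessments are repeated every 5 weeks", and its assessment table has "6MWT with pre & post Borg Scale (two times per clinic visit"). Section 8.4 adds that TUG is also done twice per visit. The home 6MWT and TUG are weekly (8.3, 8.5). The Summary expects symptoms and functional capacity to fluctuate during the five-week baseline, and expects the training that follows to change capacity.

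**The concern.** Two features of the comparison look wrong.

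- **Test.** Read with the list in 2.2, the single benchmark sets the repeatability of a TUG time against the repeatability of a six-minute distance. That does not show whether the TUG estimator is as repeatable as the clinic TUG. For the walking measurements, no clinic test in 10.3 plays the same role at all.
- **Interval.** Reliability normally falls as the gap between repeats grows. The only gap that 10.3 mentions for the estimators is one the clinic schedule does not contain.

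At stake is how a secondary endpoint is read. A statement that an estimator is more or less repeatable than the clinic test could reflect which clinic pairs were chosen rather than the estimator.

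**Working it through.** The documents give no ICC, margin or power for test-retest reliability, so there is no stated figure to reproduce. Tables 1 and 2 of section 4.4 cover other analyses.

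**Step 1: test.**

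| Algorithm (2.2) | Comparator in 10.3 | Same test in clinic? |
|---|---|---|
| 6MWT estimators (two) | in-clinic 6MWT | yes, twice per visit |
| TUG estimators (two) | in-clinic 6MWT | TUG, twice per visit, not used for this purpose |
| Free-living walking measurements | in-clinic 6MWT | none named |

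This mismatch needs no assumption beyond taking the list in 2.2 to be the one that 10.3 omits.

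**Step 2: intervals.** With two tests per visit and visits five weeks apart, clinic repeats exist at the same day, at about 5 weeks, and at about 10 and 15 weeks. Any pair that includes Visit 3 or Visit 4 spans training that is expected to change capacity, so it is not a stable retest. That leaves same-day pairs and Visit 1 versus Visit 2. Neither is one week.

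**Step 3: illustration of the interval effect.** Let a score be a stable person effect (variance B), plus a fluctuation with weekly autocorrelation r (variance W), plus test error (variance E), with B + W + E = 1 and no systematic shift between repeats. Then

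ICC at a lag of L weeks = B + W × r^L.

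Give the estimator and the clinic test identical properties, so that any gap comes from the interval alone. W, E and r are assumptions.

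With W = 0.10, E = 0.10 (so B = 0.80) and r = 0.6:

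- same day: 0.80 + 0.10 = 0.900
- one week: 0.80 + 0.10 × 0.6 = 0.860
- five weeks: 0.80 + 0.10 × 0.6^5 = 0.80 + 0.10 × 0.078 = 0.808

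A weekly estimator looks 0.040 worse than the same-day benchmark and 0.052 better than the five-week benchmark, although it is equally reliable.

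E cancels from both gaps. They are W(r − 1) against same-day pairs and W(r − r^5) against five-week pairs. For W from 0.05 to 0.20 and r of 0.3, 0.6 and 0.8:

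- against same-day pairs: from 0.05 × (0.8 − 1) = −0.010 to 0.20 × (0.3 − 1) = −0.140
- against five-week pairs: from 0.05 × (0.3 − 0.002) = +0.015 to 0.20 × (0.6 − 0.078) = +0.104

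If W = 0, both gaps are 0.

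**Step 4: matched pairing.** With the same lag on both sides the gap is 0 for every W, E and r. If the first and last home tests before Visit 2 are nearer four weeks apart than five, the remaining gap is W(r^4 − r^5). In the worked case this is 0.10 × (0.130 − 0.078) = 0.005. The largest value over the same range is 0.20 × (0.410 − 0.328) = 0.016.

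**The case against.** The strongest reply is that 10.3 gives the weekly interval only as an example. Estimates from the start and end of the Visit 1 to Visit 2 period can be paired and set against clinic 6MWT at Visit 1 versus Visit 2. For the two 6MWT estimators this matches the test and, closely, the interval, and the text allows it. This stands. A reader might infer that the comparison is biased however it is carried out; the documents do not support that.

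Other points also carry weight:

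- The interval effect needs true within-person fluctuation. The Summary expects some but gives no size.
- An ICC over all weekly repeats in the baseline period would mix lags of one to about four weeks, which narrows the gap against five-week clinic pairs.
- No success criterion is attached to this endpoint, so nothing passes or fails on it.
- The ICC has no units, so a 6MWT benchmark for TUG is not like for like but is not wholly without content. The validity of the TUG estimators is assessed separately against in-clinic TUG (8.1.2, 10.3).

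These points limit the size and consequence of the problem without removing it. The matched reading has to be constructed by the analyst, while the one interval that 10.3 mentions has no clinic match. No choice of interval turns 6MWT into a TUG comparator.

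**Conclusion.** The concern holds in two parts of different strength.

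The comparator is wrong for the TUG estimators and has no direct meaning for the walking measurements. This follows from 10.3 and 2.2 together. It is more than missing detail, because 10.3 names a comparator and that comparator does not fit, while the fitting one for TUG is already collected.

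The interval problem is conditional. If capacity fluctuates, a weekly estimator that is exactly as reliable as the clinic test would tend to look worse against same-day pairs and better against Visit 1 versus Visit 2, so the direction depends on a choice that the plan leaves open. The gaps of 0.01 to 0.14 and 0.015 to 0.104 rest entirely on assumed variance shares and autocorrelations. The true size cannot be found from the documents and could be zero. For the 6MWT estimators the bias is avoidable, but the plan should require the matched pairing rather than merely permit it.

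This is a descriptive secondary endpoint. Neither the co-primary ICC tests nor the sample size depends on it.

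**What to change.** In the COPD part of section 10.3:

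1. Insert the list of algorithms from 2.2, and state the reliability statistic and its form.
2. Benchmark the two 6MWT estimators against in-clinic 6MWT, and the two TUG estimators against in-clinic TUG.
3. For both, use Visit 1 versus Visit 2, before training. Set it against the estimates from the home weeks nearest those two visits, in the same participants. State how the two same-day clinic tests at each visit are handled, in the same way at both visits.
4. Report the week-over-week ICCs between Visits 1 and 2, and the reliability of the free-living walking measurements, separately and without the clinic 6MWT benchmark.

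The cost is revised wording and a little more analysis on data that the schedule already collects. No visit, test or participant is added.

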10.4 Other Statistical Considerations

Participants' disposition, device use compliance, and data availability will be summarized for participants enrolled in the study. Demographic and baseline characteristics will be summarized for participants in the Full Analysis Set.

11. ETHICAL CONSIDERATIONS

11.1 Regulation statement

This clinical study involving human subjects are conducted pursuant to the following codes:

- The Declaration of Helsinki 2007-2008 and its subsequent amendments;
- Directive 2001/20/EC of the European Parliament and of the Council of 4 April 2001; on the approximation of the laws, regulations and administrative provisions of the Member States relating to the implementation of good clinical practice (GCP);
- The Medical Research Involving Human Subjects Act (WMO);
- ICH E6, International Conference of Harmonization (ICH) guideline for Good Clinical Practice; MDR(EU) 2017/745;
- EN ISO 14155:2020; and
- General Data Protection Regulation 2018 (GDPR), in Dutch the 'Algemene verordening gegevensbescherming' (AVG).

Any additional requirements imposed by the METC or regulatory authority shall be followed.

11.2 Recruitment and consent

The procedure for recruitment and consent is described in paragraph 7.2. Participants are recruited by participating physiotherapists; either newly referred people with COPD and PD or people who are already treated by the physiotherapist but haven't received aerobic exercise training in the last 6 months are potentially eligible. Potentially eligible participants are asked by the physiotherapist if they are interested in participating in this study. If so, they receive the information letter. One week after receiving this letter, a researcher from Radboudumc calls the person. During this call, the person can ask questions and the researcher checks if the person fulfills the inclusion criteria. When eligible and willing to participate, an appointment for the first in-clinic assessment is made. Before participants come to the first clinic visit, participants will receive an email to create an account in the Baseline Platform that they will use for completion of surveys and getting notifications for upcoming visits. After creating the account, they will review and sign an electronic screening consent form to provide contact information and to give permission to contact their treating physician.

At the start of the first in-clinic visit, the IRB approved informed consent form is signed by both the participant and the physiotherapist on paper. The participant receives a copy of the form.

11.3 Objection by minors or incapacitated subjects (if applicable)

Not applicable (study only includes adults able to provide informed consent).

11.4 Benefits and risks assessment, group relatedness

There are limited risks to the participant during the data collection. Potential risks relate to the in-clinic assessments and the unsupervised home assessments. A structured risk and benefit analysis is available in section 12. The participant will not directly benefit the study. However, they do receive 10 weeks of personalized physiotherapy as part of this protocol.

Because they have an indication for physiotherapy, they will also receive a physiotherapeutic intervention if they choose not to participate in this study.

Importantly, participants will indirectly benefit from the study. The remote measurement of physical capacity, physical activity and potentially disease status are novel insights being derived and measured by the data generated by the participants wearing the sensors. This may, in the future, have a positive impact on remote disease monitoring and more precise and personalized disease management. In turn, this potentially provides future benefits for all people affected by the disease. Prospectively, measurements from the Verily Study Watch could supplement and enhance the information available to the physician, providing continuous measurement and quantitative (rather than subjective) data. The device detects important physiologic parameters that are expected to change with disease conditions or behavioral patterns (e.g. electrodermal activity, physical movement of the body in three dimensions [acceleration], skin temperature, heart rhythm, etc.). In addition to collecting data, the device also functions as a wristwatch.

11.5 Compensation for injury

The sponsor/investigator has liability insurance in accordance with article 7 of the WMO. Additionally, the sponsor has insurance in accordance with the legal requirements in the Netherlands (see Article 7 WMO). This insurance provides coverage in the event of damage to research subjects as a result of the study. This coverage applies to damage that becomes apparent during the study, up to and within, 4 years after the end of the study.

11.6 Incentives (if applicable)

The only potential incentive that participants receive as part of this study is enhancement of the treatment already being provided as part of their physiotherapy that is covered by the participant's health insurance.

11.7 Handling and storage of data and documents

11.7.1 Data Protection

Radboudumc will use Verily's proprietary online platform (i.e. Baseline Platform) to collect clinical, behavioral, psychological, self-reported, other health-related data and demographic information. The Baseline Platform includes a proprietary Electronic Data Capture system, referred to as EDC, or eSource. Participants will be assigned a unique identifier (code) by the Baseline Platform.

The participant must be informed that his/her personal study-related data will be used by the sponsor in accordance with local data protection law. The level of disclosure must also be explained to the participant. All data used in the analysis and reporting of this evaluation will be pseudonymized and used without identifiable reference to the study participant.

The participant must be informed that his/her medical records may be examined by Clinical Quality Assurance auditors or other authorized personnel appointed by the sponsor, by appropriate IRB members, and by inspectors from regulatory authorities. Sponsor may provide access to study data to its scientific collaborators to perform further explorative analysis.

11.7.2 Privacy of Personal Data

The collection and processing of personal data from participants enrolled in this study will be limited to the data that are necessary to fulfill the objectives of the study. This data will be collected and processed with adequate precautions to ensure confidentiality and compliance with applicable data privacy protection laws and regulations. Appropriate technical and organizational measures to protect the personal data against unauthorized disclosures or access, accidental or unlawful destruction, or accidental loss or alteration must be put in place. Study personnel whose responsibilities require access to personal data agree to keep the identity of participants confidential.

The informed consent obtained from the participant describes the legal basis for the processing of personal data, i.e. the legal basis for collecting and processing data for this study is for research purposes as the legitimate interest. This is the lawful basis for the Investigator/institution to have direct access to participant's original source data for study-related monitoring, audit, IRB review, and regulatory inspection. We must also describe the technical and organizational measures we are using to protect the privacy, security, and confidentiality of this data as part of processing this data for research purposes.

The informed consent also addresses the transfer of the data to other entities and to other countries, both within and outside of the EU.

The participant has the right to request through the Investigator access to his or her personal data and with some limitations related to research, the right to request rectification of any data that are not correct or complete. Reasonable steps will be taken to respond to such a request, taking into consideration the nature of the request, the conditions of the study, and the applicable laws and regulations.

11.7.3 Data Quality Assurance

All participant data relating to the study will be recorded on printed or electronic CRF or ePRO, unless transmitted to the sponsor or designee electronically (e.g., device data). Verily uses a proprietary online portal ("Baseline Platform") for collecting clinical, behavioral, psychological, self-reported, and other health-related data from participants. Additionally, Verily utilizes a proprietary Electronic Data Capture system, referred to as EDC, or eSource. Verily is responsible for the data management activities of this study, including data quality review. The sponsor assumes accountability for actions delegated to other individuals. The sponsor will review data to ensure key elements are collected, as it concerns the study. In case it should become necessary, additional monitoring instructions can apply.

